The primary objective is to evaluate the effects of EPI-589 on safety as assessed by occurrence of drug-related serious adverse events in subjects with ALS.

B. Secondary Objectives

The secondary objectives are to evaluate the effects of EPI-589 in subjects with ALS on:

- 1. Glutathione cycle biomarkers as measured in blood, cerebral spinal fluid, and urine
- 2. Disease progression as assessed by ALS Functional Rating Scale-Revised
- 3. Respiratory function as assessed by pulmonary function tests and capnography
- 4. Failure to thrive as measured by body weight
- 5. Swallowing as assessed by change in water and solid swallowing tests
- 6. Speech as assessed by speech evaluation
- 7. Muscle function as assessed by handheld dynamometry
- 8. Drug plasma concentration measurements
- 9. Hematology, blood chemistry, electrocardiogram

V. INVESTIGATIONAL PLAN

A. General Schema of Study Design

After study enrollment, baseline assessments will be performed. Subjects participate in a 30-day run-in phase to establish baseline ALS disease-related clinical and biomarker features. EPI-589 will then be administered for 3 months, unless discontinued for safety or tolerability issues. All subjects will then be followed for an additional 90 days to determine long-term effects, duration of response to treatment, and potential effects of EPI-589 therapy on known disease trajectory.

A1. Screening Phase

Suitable candidates for the trial will receive a short overview of the study by the Investigator's staff and, if interested, will undergo Screening. The Investigator will inform each prospective subject of the nature and details of the study, explain the potential risks and must obtain written informed consent from the subject or their legally authorized representative prior to performing any study related procedures.

A2. 30-Day Run-in Phase

Once eligibility is confirmed, the subject will be enrolled in the study and the ALS Functional Rating Scale-Revised (ALSFRS-R) measurements and CNS, urine-based and blood-based glutathione cycle biomarkers, will be collected.

A3. Baseline

ALSFRS-R, lumbar puncture, swallowing, speech, handheld dynamometry, blood-based biomarkers, urine biomarkers, and clinical measurements will be collected.

A4. Treatment Phase

EPI-589 dosing will start on Day 1. Subjects will self-administer EPI-589 at a dose of 500 mg BID.

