Blood biomarker, urine biomarker, clinical measurements, and pharmacokinetic plasma concentrations will be collected at Day 29 (+/-3 days) and Day 85 (+/- 3 days). Lumbar puncture will be collected at Day 85 (+/- 3 days).

A5. Study Withdrawal Phase

Closeout data will be collected over a 90-day period, during the Withdrawal Phase.

ALSFRS-R, blood-based biomarkers, urine-based biomarkers, and physical exam including weight and vital signs will be collected at Month 4.

ALSFRS-R, swallowing, speech, handheld dynamometry, blood-based biomarkers, urine-based biomarkers, and physical exam including weight and vital signs will be collected at Month 6.

Adverse events reported as ongoing during the Withdrawal Phase, and any concomitant medications associated with such events will be followed for 30 days. Month 5 AE and concomitant medication assessments can be conducted by telephone.

B. Randomization and Blinding

This is an open-label study.

C. Study Duration, Enrollment and Number of Sites

C1. Duration of Subject Treatment

Subjects will participate in a 30-day run-in phase to establish baseline ALS disease-related clinical and biomarker features. EPI-589 will then be administered for 3 months unless discontinued for safety or tolerability issues. Subjects will return to the clinic for assessments at two time points during a 90-day withdrawal period.

C2. Total Number of Study Sites/Total Number of Subjects Projected

This study will be conducted at the California Pacific Medical Center, San Francisco, CA. Additional sites may be added in order to decrease enrollment timelines.

Projected enrollment is approximately 20 subjects with ALS.

D. Study Population

D1. Inclusion Criteria

- 1. Diagnosis of possible, probable, laboratory supported probable or definite amyotrophic lateral sclerosis (ALS) by El Escorial Criteria.
- 2. Male or female between 21 and 70 years of age
- 3. Forced vital capacity (FVC) \geq 70% of predicted
- 4. Onset of weakness within 3 years as documented in clinical records
- 5. Agreement to use contraception if within reproductive years
- 6. Willingness and ability to comply with study procedures
- 7. Stable regimen of dietary supplements for 30 days prior to enrollment
- 8. Abstention from use of other investigative or non-approved drugs
- 9. Subjects on riluzole must be on a stable dose for at least 30 days prior to study enrollment.
- 10. Subject must be able to swallow 0.375 x 0.700 inch tablets.

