- 2. 12-Lead ECG
- 3. Pulmonary function assessment and capnography
- 4. Hematology including coagulation and serum chemistry*
- 5. Weight and vital signs
- 6. Pregnancy test (women of childbearing potential)
- 7. Glutathione cycle blood, urine and CNS biomarkers
- 8. C-SSRS
- 9. ALS Functional Rating Scale-Revised
- 10. Water and solid swallowing tests
- 11. Speech assessment
- 12. Handheld dynamometry

EPI-589 will be dispensed to the subjects along with the dosing diary. Subjects will self-administer EPI-589 at a dose of 500 mg BID starting from Day 1.

* Screening values can be used if done within one month of baseline and if completed under fasted conditions

B2. Study Visit Assessments

Adverse events and concomitant medication information will be reviewed and assessed at each visit.

Clinic Visits: Month 1 and Month 3

The following will be assessed or performed at the Month 1 (Day 29 +/-3 days) clinic visit:

- 1. Physical examination
- 2. 12-lead ECG
- 3. Pulmonary function assessment and capnography
- 4. Hematology including coagulation and serum chemistry
- 5. Weight and vital signs
- 6. Pregnancy test (women of childbearing potential)
- 7. Glutathione cycle blood, urine, and CNS biomarkers
- 8. ALS Functional Rating Scale-Revised
- 9. Drug plasma concentration measurements*

The following will be performed at the Month 3 (Day 85 +/- 3 days) clinic visit:

- 1. Physical examination
- 2. 12-lead ECG
- 3. Pulmonary function assessment and capnography
- 4. Hematology including coagulation and serum chemistry
- 5. Weight and vital signs
- 6. Pregnancy test (women of childbearing potential)
- 7. Glutathione cycle blood, urine, and CNS biomarkers
- 8. Drug plasma concentration measurements*
- 9. ALS Functional Rating Scale-Revised
- 10. Water and solid swallowing tests
- 11. Speech assessment
- 12. Handheld dynamometry

Drug accountability and compliance: Subjects should bring the study medication and the dosing diary at the Month 1 and Month 3 visits. All the used and unused study medication should be returned and reconciled at the Month 3 visit.

Month 2 Assessments

Month 2 assessments can be conducted by telephone and will include review of concomitant medications and AEs.

B3. Early Termination of Study Medication

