Subjects who terminate from the study after receiving first dose and prior to the completion of the treatment phase should have an end of study visit as soon as possible. All the Month 3 visit assessments should be completed at this visit.

C. Withdrawal Phase and Study Completion

Month 4 Clinic Visit (Day 113 +/- 1 Week)

- 1. Physical examination
- 2. Weight and vital signs
- 3. Blood-based biomarkers
- 4. Urine-based biomarkers
- 5. C-SSRS
- 6. ALS Functional Rating Scale-Revised
- 7. AEs and SAEs
- 8. Concomitant medications

^{*}Pharmacokinetics: Plasma concentration samples will be collected at 0-hour and 0.5, 1, 2, 4, 6, 8, and 12 hours post-dose at the Month 1 and Month 3 clinic visits.

Month 5 Assessments

Month 5 assessments may be conducted by telephone.

- 1. AEs and SAEs
- 2. Concomitant medications

Month 6 Clinic Visit (Day 169 +/- 1 Week)

- 1. Physical examination
- 2. Weight and vital signs
- 3. Glutathione cycle blood-based biomarkers
- 4. Glutathione cycle urine-based biomarkers
- 5. ALS Functional Rating Scale-Revised
- 6. Water and solid swallowing tests
- 7. Speech assessment
- 8. Handheld dynamometry
- 9. Pulmonary function tests and capnography
- 10. AEs and SAEs
- 11. Concomitant medications

Subjects who have an ongoing AE at the time of study completion will be followed for up to 30 days, until the event resolves, or until the Sponsor and the Investigator agree that further follow-up is not medically necessary.

D. Unscheduled Visits

If a subject returns to the clinic outside of the normal treatment visit windows, assessments will be made at the Investigator's discretion. All relevant unscheduled visit data will be recorded in the CRF using the supplemental visit CRF pages.

E. Concomitant Medication

Any medication taken by a subject \leq 60 days prior to enrollment and during the course of the study and the reason for use of the medication will be recorded on the case report form (CRF). During screening, each subject will be instructed to report the use of any medication to the Investigator. Subjects will also be instructed about the importance of not taking any medication throughout the study (including over-the-counter [OTC] medications) without first consulting the Investigator.

F. Prohibited Medications

The following are prohibited while the subject is on study treatment:

- 1. Use of antioxidants, specifically vitamins E and C beyond the recommended daily allowance

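### The limit on antioxidant vitamins starts with dosing on Day 1, after the Day 0 glutathione samples, so some subjects' baseline-to-Month 3 change may include a forced change in vitamin use

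*Protocol*

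**What the plan says.** The first item in Protocol section VI.F (Prohibited Medications) is "Use of antioxidants, specifically vitamins E and C beyond the recommended daily allowance". The lead-in to the list sets its window: "The following are prohibited while the subject is on study treatment". The second item, on other ALS trials, carries its own longer window, starting 3 months before the Screening Visit. The antioxidant item has none.

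Section VI.B1 lists "Glutathione cycle blood, urine and CNS biomarkers" among the baseline assessments and then has subjects take "EPI-589 at a dose of 500 mg BID starting from Day 1". The schedule in section II shows Day 0 Baseline as a column separate from the Treatment Phase.

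On entry, inclusion criterion 7 (section V.D1) asks for "Stable regimen of dietary supplements for 30 days prior to enrollment". It sets no dose limit, and none of the 12 exclusion criteria mentions antioxidants. Section VI.E has all medication recorded from 60 days before enrollment and tells subjects about "not taking any medication throughout the study (including over-the-counter [OTC] medications) without first consulting the Investigator".

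Section VIII.A describes a subject-controlled, open-label study in which biomarker change is calculated from baseline to Month 3. Section III.B gives confirmation of target engagement through glutathione-cycle markers as the study's purpose.

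**The concern.** A within-subject contrast without a control arm can be read as a drug effect only if nothing else changes systematically between the two samples. For a stable user of high-dose vitamin E or C, this protocol requires such a change. Criterion 7 keeps supplement use steady up to enrollment, and section VI.F then obliges the user to cut back when EPI-589 starts. The vitamin change and the drug start coincide, and no concurrent group is available to separate them.

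What is at stake is the glutathione-cycle evidence of target engagement in blood, urine and CSF. If the vitamins affect these markers, an affected subject's change could be too large or too small. The primary endpoint, drug-related serious adverse events, is not involved.

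**Working it through.** **Timeline.** The protocol states no figure to reproduce, so the first check sets the rule against the sampling times for a stable user above the allowance.

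| Time | Glutathione samples (schedule, section II) | High-dose vitamins E and C |
|---|---|---|
| Run-in, about Day -30 | Blood, urine | Not restricted |
| Day 0 | Blood, urine, CSF | Not restricted |
| Month 1 (Day 29) | Blood, urine | Prohibited |
| Month 3 (Day 85) | Blood, urine, CSF | Prohibited |
| Months 4 and 6 (Days 113, 169) | Blood, urine | Not restricted |

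A site may ask a user to stop earlier, but nothing requires it. The same window lets users restart during the withdrawal phase, which affects the Month 4 and Month 6 samples intended to show duration of response.

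For CSF the protocol is inconsistent. The schedule has lumbar puncture at Day 0 and Month 3 only, and V.A4 says "Lumbar puncture will be collected at Day 85 (+/- 3 days", with no Month 1 puncture. But V.A2 (run-in) says "CNS, urine-based and blood-based glutathione cycle biomarkers, will be collected", and VI.B2 also lists CNS biomarkers at Month 1. This is a side issue, because the Day 0 to Month 3 CSF contrast spans the start of the limit on either reading.

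**Size.** Only n = 20 comes from the protocol. The assumed inputs are:
- k, the number of users who cut back at Day 1;
- d, the marker shift per user, in units of the between-subject SD, taken as equal at both times;
- rho, the Day 0 to Month 3 correlation, set at 0.5 or 0.8.

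Bias in the mean change = k × d / 20.

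Standard error of the mean change = sqrt(2(1 − rho)/20):
- rho = 0.5: sqrt(0.05) = 0.224 SD
- rho = 0.8: sqrt(0.02) = 0.141 SD

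| k × d | Example | Bias (SD) | Bias / SE, rho 0.5 | Bias / SE, rho 0.8 |
|---|---|---|---|---|
| 1 | 2 users at 0.5, or 4 at 0.25 | 0.05 | 0.22 | 0.35 |
| 2 | 4 users at 0.5, or 2 at 1.0 | 0.10 | 0.45 | 0.71 |
| 6 | 6 users at 1.0 | 0.30 | 1.34 | 2.12 |

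Only the product k × d matters. Bias reaches half a standard error when k × d = 0.5 × SE × 20, which is 1.4 (rho 0.8) to 2.2 (rho 0.5). It reaches one standard error at 2.8 to 4.5.

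The table assumes that all shifts go the same way. With 4 users at 0.5 SD, three up and one down, bias is (3 − 1) × 0.5 / 20 = 0.05 SD, half the same-direction value.

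**The case against.** The strongest reply is that harm is not shown. Some subjects must exceed the allowance, the vitamins must shift these markers, and the shift must still be present at Day 85. The protocol states none of this and gives no reason for its own prohibition. That stands. It is why every magnitude above is an illustration, and the largest case has no support in the document. The standard error is only a yardstick, since the protocol specifies no biomarker test.

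A second reply is that section VI.E already identifies users, so with about 20 subjects their changes can be read separately, and an analysis plan could provide for that. This is partly right: recording use shows who is affected. It does not prevent the change in vitamin use, and an analysis plan cannot alter what subjects take before Day 0. A user who stays off the vitamins also gives off-drug blood and urine samples at Months 4 and 6, but no CSF.

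A third reply is that stopping vitamins after the run-in sample makes that sample non-comparable with Day 0, although the run-in exists to establish baseline. That is a real cost, but a small one: it affects only users who stop, and the planned contrast starts from baseline.

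Listing the baseline visit under the Treatment Phase heading in VI.B does not rescue the rule. The schedule separates the two, and the drug starts on Day 1.

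**Conclusion.** The concern holds as a minor design point. Followed exactly, the protocol admits stable high-dose users, allows their Day 0 samples on the vitamins, and requires them to be at or below the allowance by Month 3, within an uncontrolled contrast. That rests on the text alone.

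Whether bias results depends on two unknowns, the number of users and the vitamins' effect on the markers. Its direction is also unknown. Under the assumptions shown, bias runs from zero to 0.30 SD. Confidence is medium, and the case for acting rests mainly on how little the change costs.

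**What to change.** Amend section VI.F item 1 so that the limit begins at enrollment, immediately after the run-in sample, and continues at least through the Month 3 sample. Extending it through Month 6 is preferable, so that restarting does not blur duration of response. Ask that other supplements be held stable over the same period. This gives about 30 days (27 to 33) at or below the allowance before Day 0. State that for users who stop at enrollment the reference is Day 0, not the run-in value.

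For subjects already enrolled, use the concomitant-medication records to flag changes in antioxidant use, and repeat the biomarker summaries without those subjects.

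**Cost.** Amendment wording only: no extra visit, no delay to treatment and no exclusion of users. The restriction lengthens from 85 days (Day 1 to Day 85) to about 115 (30 + 85), or about 199 (30 + 169) if carried to Month 6. The run-in sample no longer helps set baseline for users who stop. The remedy also relies on about 30 days being long enough for the markers to settle, which the protocol does not address. Leaving out 2, 4 or 6 of 20 subjects enlarges the standard error by sqrt(20/(20 − k)) − 1, which is about 5%, 12% or 20%.

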- 2. Participation 3 months prior to the Screening Visit and for the duration of study in a trial of a device, drug or other therapy for ALS

G. Subject Withdrawals

Subjects may be withdrawn from the study at any time for reasons including the following:

- 1. At their own request or at the request of their legally authorized representative
- 2. If, in the Investigator's opinion, continuation in the study would be detrimental to the subject's well-being
- 3. For failure to comply with the Protocol (i.e., dosing compliance, failure to complete diaries as instructed, failure to keep scheduled appointments)
- 4. At the specific request of the Sponsor (or designee).
- 5. Additional protocol specific reasons

In all cases, the reason for withdrawal must be recorded in the CRF and in the subject's medical records. If the reason is not known, the subject must be followed to establish whether the reason was due to an AE and, if so, this must be reported in accordance with the procedures in Section X.B.

Evaluations must be performed on all subjects who participate but do not complete the study according to protocol. Dropouts may be replaced at the request of the Sponsor. The Investigator will make every effort to contact subjects lost to follow-up.

Every effort will be made to follow subjects who have an ongoing AE at the time of withdrawal until the event resolves, or until the Sponsor and the Investigator agree that further follow-up is not medically necessary.

VII. STUDY ENDPOINTS AND EVALUATIONS

A. Primary Endpoint

To evaluate the effects of EPI-589 on safety as assessed by occurrence of drug-related serious adverse events in subjects with ALS following three months of EPI-589 therapy.

B. Secondary Endpoints (Efficacy)

- 1. Blood-based biomarkers
- 2. CNS-based biomarkers
- 3. Urine-based biomarkers
- 4. Disease progression as assessed by ALS Functional Rating Scale-Revised
- 5. Respiratory function as assessed by pulmonary function tests and capnography
- 6. Failure to thrive as measured by body weight
- 7. Swallowing as assessed by change in water and solid swallowing tests
- 8. Speech as assessed by speech evaluation
- 9. Muscle function as assessed by handheld dynamometry
- 10. Drug plasma concentration measurements

C. Secondary Endpoints (Safety)

- 1. Routine assessments of AEs and SAEs
- 2. Dose limiting toxicities
- 3. Routine serum chemistries with liver function tests
- 4. Routine hematology tests with coagulation tests

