In this subject-controlled, open label study the incidence of drug related SAEs in addition to changes from baseline to Month 3 for disease-relevant peripheral and CNS biomarkers as well as clinical measures will be calculated for each subject. In addition, changes in the ALSFRS-R will be measured three months following withdrawal of therapy and compared with disease natural history data to determine effects of EPI-589 on disease trajectory.

A1. Analysis Populations

Demographic characteristics and baseline efficacy data will be presented and summarized for all subjects in the efficacy intent-to-treat (EITT) population. Demographic information will also be summarized for the safety population. No formal statistical comparisons will be made for either the EITT or Safety populations.

B. Efficacy Analysis

B1. Efficacy Variables

The efficacy variables in this study are

- 1. Blood-based glutathione cycle biomarkers
- 2. Urine-based glutathione cycle biomarkers
- 3. Disease progression as assessed by ALS Functional Rating Scale-Revised
- 4. Respiratory function as assessed by pulmonary function tests and capnography
- 5. Failure to thrive as measured by body weight
- 6. Swallowing as assessed by change in water and solid swallowing tests
- 7. Speech as assessed by speech evaluation
- 8. Muscle function as assessed by handheld dynamometry
- 9. Drug plasma concentration measurements

C. Safety Analysis

The primary objective of this study is to evaluate the effects of EPI-589 safety as assessed by occurrence of drug-related serious adverse events in subjects with ALS. Assessment of safety will include calculating the overall number of subjects (by absolute number and percentage) with a particular AE. Safety will also be evaluated through examining clinical laboratory data (including chemistry and hematology and coagulation information) and physical examination findings, including vital signs obtained throughout the course of the study. A medical monitor will provide study oversight.

D. Sample Size

Approximately 20 subjects will be enrolled in this exploratory biomarker study.

IX. STUDY MEDICATION

A. Description

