EPI-589 is presented as an instant release solid oral tablet. Each tablet contains 250 mg of EPI-589 and the following compendial excipients: lactose monohydrate, microcrystalline cellulose, polyvinylpyrrolidone, crospovidone, and magnesium stearate. Each tablet is film-coated with Opadry® II yellow. The tablets are yellow-colored and oval shaped with a total target weight of 824 mg. The tablets are packaged at 28 tablets per bottle in high density polyethylene (HDPE) pharmaceutical wide mouth containers, induction sealed, and closed with a child resistant closure. Each container is labeled with appropriate product information meeting current regulatory requirements.

B. Packaging

B1. Labeling

Each container is labeled with appropriate product information meeting current regulatory requirements that comply with 21 CRF 312.6.

B2. Dosage Form

The EPI-589 drug product will be provided in a 250-mg tablet formulation.

B3. Dispensing

Tablets are packaged in white round HDPE wide mouth containers. Each container holds 28 tablets without desiccant. Each container is sealed with an induction seal held in place with a child resistant closure. The packaged tablets are stored at controlled room temperature 20° to 25°C (68° to 77°F). (See United States Pharmacopeia [USP].)

B4. Treatment Compliance and Adherence

Study medication will be counted to assess compliance during each scheduled clinic visit. Subjects who take ≥ 80 percent of the prescribed doses and no more than 100 percent will be considered compliant. Subjects who fall outside the boundaries of these thresholds will be counseled and re-instructed on proper dosing procedures. Medication compliance will be recorded on the CRF for each visit after reconciliation with subject-completed dosing diaries and returned used drug supply.

B5. Drug Accountability

Dosing information will be captured on a subject Dosing Diary Form. This form is part of the study source documentation and will be utilized as a source for the completion of CRFs

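### Dosed subjects can be withdrawn without Month 4 or Month 6 ALSFRS-R assessments, although V.A promises 90 more days of follow-up for all, and replacement can mask the loss

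*Protocol*

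**What the plan says.** **Withdrawal and replacement (Protocol VI.G).** The list of reasons is open: "Subjects may be withdrawn from the study at any time for reasons including the following". Item 3 reads "For failure to comply with the Protocol (i.e., dosing compliance, failure to complete diaries as instructed, failure to keep scheduled appointments" and item 4 reads "At the specific request of the Sponsor (or designee", with no criterion attached to item 4. The same section states: "Dropouts may be replaced at the request of the Sponsor". It sets no limit by dosing status, reason, timing or number. It does require the reason for withdrawal to be recorded and non-completers to be evaluated, without saying which evaluations or when.

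**After early termination (VI.B3).** The heading concerns stopping study medication, but the text concerns subjects who leave the study after the first dose and before the end of treatment. They should have one end-of-study visit, as soon as possible, with the Month 3 assessments. Month 4 and Month 6 are not mentioned.

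**Follow-up (V.A).** After the treatment period, which may end early for safety or tolerability, all subjects are to be followed for another 90 days.

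**Compliance (IX.B4).** Outside the 80 to 100 percent range: "Subjects who fall outside the boundaries of these thresholds will be counseled and re-instructed on proper dosing procedures".

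**Analysis (VIII.A, VIII.C).** The design is described thus: "In this subject-controlled, open label study the incidence of drug related SAEs in addition to changes from baseline to Month 3". The ALSFRS-R is also measured three months after therapy is withdrawn and compared with natural history data. Safety is summarised by "calculating the overall number of subjects (by absolute number and percentage) with a particular AE".

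**The concern.** The ALSFRS-R comparison with natural history has no concurrent arm to absorb selective loss. If subjects who progress faster or tolerate the drug poorly are more likely to leave, and leaving ends their assessments, the Month 6 set leans toward slower progressors. That lean points the same way as a benefit.

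V.B states "This is an open-label study", and under XI.B the sponsor monitors the trial itself, so the party that may request withdrawal and replacement can see a subject's course when it does so. A replacement then supplies the Month 6 value that the departed subject does not. The count looks complete although the loss has occurred.

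This is a conduct matter. An analysis plan can decide how to handle missing assessments, but it cannot recover assessments that sites were never asked to make.

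**Working it through.** There is no stated calculation to reproduce: VIII.D gives approximately 20 subjects, with no power, effect size or dropout rate. The check is mainly a comparison of sections.

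**1. Which visit carries the comparison.** Month 3, the end of treatment, is Day 85 (VI.B2) and Month 6 is Day 169 (VI.C). 169 − 85 = 84 days, so the assessment three months after therapy is the Month 6 visit.

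**2. What each section gives a dosed subject who stops after Month 1.**

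| Section | Consequence |
|---|---|
| IX.B4 (if the cause is compliance) | Counselling and re-instruction |
| VI.G items 3 and 4 | May be withdrawn from the study |
| VI.B3 | One visit with Month 3 assessments, as soon as possible |
| V.A | Followed for an additional 90 days |
| VI.G | May be replaced at the sponsor's request |

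The Schedule of Assessments places the ALSFRS-R after baseline at Months 1, 3, 4 and 6, so a full-course subject has four values. Under VI.B3 this subject has two (Month 1 and the early end-of-study visit) and neither of the two from the withdrawal phase. Under V.A the follow-up would continue. The protocol does not say which section governs, nor does it separate stopping the drug from leaving the study.

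**3. How replacement masks the gap.** Assume that 4 of 20 dosed subjects leave, all are replaced and every replacement completes.
- Without replacement: 16 of 20 dosed have Month 6 data, 16/20 = 80%.
- With replacement: 20 of 24 dosed have Month 6 data, 20/24 = 83.3%.

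The same four subjects are missing in both cases. With replacement, the Month 6 count equals the planned number.

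**4. How large the effect of the loss could be.** Assume that ALSFRS-R change is normally distributed, that the k subjects lost are exactly the k fastest progressors of 20, and that any replacements resemble those who remain. With q = k/20 and c the (1 − q) quantile of the standard normal, the mean of the remaining subjects shifts by φ(c)/(1 − q) SD toward slower decline.

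| k lost | q | Shift (SD) |
|---|---|---|
| 1 | 0.05 | 0.11 |
| 2 | 0.10 | 0.20 |
| 3 | 0.15 | 0.27 |
| 4 | 0.20 | 0.35 |

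For each k this is the extreme case; loss unrelated to progression gives an expected shift of 0. The shift comes from the missing assessments. Under these assumptions it is the same with or without replacement.

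**The case against.** **No exchange of subjects is stated.** A reader might infer that a subject with toxicity can be swapped out of the safety result. The documents do not support that. VIII.A1 names a Safety and an efficacy intent-to-treat population, and no section removes a replaced subject from either. X.A has all AEs recorded in the CRF, X.C7 has SAEs reported to the sponsor within 24 hours, and VI.G requires the withdrawal reason and pursues unknown reasons for a possible AE. This stands.

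**Replacement does not itself create the bias.** It is tempting to illustrate with 4 of 20 subjects leaving, 2 of them with a drug-related SAE, and declines of 2 points per month in those four against 1 in the others. All 20 dosed then average (16 × 1 + 4 × 2)/20 = 1.2, and a completed set of 20 averages 1.0, an apparent slowing of 1 − 1.0/1.2 = 17% with 0/20 SAEs. Without any replacement, the 16 completers also average 1.0 and show 0/16. Those figures describe a completer-only analysis, which the protocol does not specify. Nor is a fall from 2/20 to 2/24 evidence of bias: it assumes that none of the four replacements has an event. This stands.

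**Replacements are not specially selected.** They meet the same entry criteria as everyone else. This stands.

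**VI.G item 3 and IX.B4 are compatible.** Counselling can come first and discretionary withdrawal later. This stands, though neither section says when one gives way to the other.

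**The link with outcome is not documented.** III.A lists dysphagia and difficulty with movement as part of progression, but no section gives the cause or frequency of missed doses. Outcome-related loss is therefore a possibility and not a stated fact.

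**V.A already follows all subjects.** This helps only in part, because VI.B3 gives early leavers a single closing visit and sites have no rule for choosing between the two sections.

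**Conclusion.** The point holds as a permitted route to outcome-related loss of the Month 4 and Month 6 ALSFRS-R data. VI.G and VI.B3 together let a dosed subject leave with one closing visit, V.A says otherwise, and unrestricted replacement can conceal the gap.

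Its size is unknown. The illustrative range is 0 to 0.35 SD for up to four losses among 20, and the upper end needs the strong assumption that the fastest progressors are exactly those lost. Early leavers should still supply the Month 3 assessments at their closing visit, so their course is not wholly unobserved.

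The protocol does not support the stronger inference that replaced subjects disappear from the safety or efficacy results. The study is exploratory, and VIII.A1 plans no formal statistical comparisons for either population. This is a cheap improvement to the conduct rules and not a defect that invalidates the design.

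**What to change.** In VI.G and VI.B3, state that:
- Dosing non-compliance, or stopping study drug, does not by itself end participation.
- Dosed subjects who still consent continue the scheduled Month 3, Month 4 and Month 6 assessments, consistent with V.A.
- Any replacement is added to, and never substituted for, a dosed subject.

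This concerns assessments only. It does not change when study drug is stopped, and the separate pregnancy provision in X.C2 needs to be cross-referenced so that the sections do not conflict. A ban on replacing dosed subjects is not needed for this purpose, and the definition of the analysis sets can be left to the analysis plan.

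The cost is protocol wording and a few visits, already in the schedule, for subjects who are off drug. VIII.D states approximately 20 subjects and no power, so no stated precision is lost.
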